Eligibility Criteria	 Willingness to comply with study procedures/requirements. Capable of giving informed consent. Diagnosis of PRP by clinical assessment and biopsy. Male age 18-99, willing to use a reliable form of birth control if sexually active with a woman who is able to become pregnant. Female age 18-99; either of non-childbearing potential or of childbearing potential who test negative for pregnancy and agree to use a reliable method of birth control or remain abstinent during the study and for at least 12 weeks following the last dose of guselkumab. Involved BSA ≥ 10% at baseline (moderate-to-severe disease). Are a candidate for phototherapy and/or systemic therapy. Willingness to travel to OHSU for all study visits, or willing/able to participate in remote videoconferencing visits with access to a computer with internet and webcam capabilities. 					
	 Exclusion criteria Known malignancy or lymphoproliferative disease (except treated basal cell skin cancer, treated squamous cell skin cancer, or treated cervical carcinoma in situ) for at least 5 years. Active, untreated, acute or chronic infection, or 					

 immunocompromised to an extent that such that participation in the study would pose an unacceptable risk to the subject. Positive for human immunodeficiency virus, hepatitis B virus, or
 Positive for human infinitionodenciency virus, nepatitis B virus, or hepatitis C virus.
 Have latent or active untreated tuberculosis (TB), a positive QuantiFERON-TB Gold test result, signs or symptoms of active TB on medical history or physical examination, or close contact with a person with active TB who have not undergone evaluation or treatment for TB. Those who are currently undergoing treatment or who have documented completed treatment for active or latent TB without re-exposures will not be excluded.
 Previous treatment with any agent that targets the interleukin 23 p19 subunit specifically.
 Systemic treatment with prednisone in the last 2 weeks, or other systemic therapies or phototherapy for PRP within the past 4 weeks or 5 half-lives prior to baseline, whichever is longer. For biologic therapies, the specific washout periods used will be: etanercept <28 days; infliximab, adalimumab, ixekizumab, or alefacept <60 days; golimumab <90 days; secukinumab <5 months; ustekinumab <8 months; rituximab or efalizumab <12 months.
 Have a known allergy or hypersensitivity to any biologic

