1. BACKGROUND

1.1. Overview of Pityriasis Rubra Pilaris (PRP) and Guselkumab

Pityriasis rubra pilaris (PRP) is a rare and poorly understood severe inflammatory cutaneous disease characterized by widespread (often full-body) erythematous plaques, skin flaking and ichthyosis, painful thickening and cracking of the palms and soles, hair loss, crumbling nails, and severe skin pruritus and burning. The most common type of PRP affects otherwise-healthy adults and may be explosive in onset. Although PRP does not affect internal organs and no quality-of-life impact studies have been published, the high degree of morbidity is perhaps best illustrated by the following colorful quotes from members of a PRP Facebook support group (with >800 members):

"All I want is normal skin... for my eyes to stop watering constantly, to take off my clothes one time and not be shrouded by a cloud of dusty skin flakes..."

"My husband can barely walk or use his hands."

"My scalp is like the Sahara Desert experiencing the dust storm of the century."

"I want my life back!!! Please."

Not surprisingly, one study showed over half of patients with PRP reporting depression (1).

While the pathogenesis of PRP is poorly understood, similarities with inflammatory pathways in psoriasis have been reported. The major effector cells present in psoriatic lesions are Th17 cells, and a recent case report showed similar overexpression of cytokines in the Th17 pathway in cutaneous lesions of PRP, including the primary effector cytokines IL-23, IL-22, and IL-17 (2). Additionally, familial cases of both psoriasis and PRP have been associated with germline gain-of-function mutations in the caspase recruitment domain family, member 14 (CARD14) gene (*3*, *4*), and cutaneous overexpression of CARD14 was observed in cases of sporadic PRP (5). CARD14 overexpression *in vitro* has also been shown to induce excess IL-23 (6).

Guselkumab is a high affinity, humanized IgG1 lambda monoclonal antibody that selectively binds the p19 subunit of IL-23. Two phase III studies of guselkumab in the treatment of psoriasis showed excellent safety and efficacy, with "clear" or "almost clear" skin ratings in 84-85% of patients at week-16 (*7, 8*).

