3.2.2. Secondary Endpoints Assessed by Investigator

- Time to improvement by 50% in the PASI score (PASI 50)
- Mean reduction in body surface area (BSA) at week-24. BSA is collected as part of the PASI assessment tool.
- Proportion of subjects achieving a Physician's Global Assessment (PGA) of 0 or 1 at week-24
- Proportion of subjects achieving a Palmoplantar Physician's Global Assessment (PPPGA) of 0 or 1 at week-24. Palmoplantar disease will be assessed separately from overall disease since it has high morbidity and may respond differently to therapy.
- Mean percentage improvement in nail involvement measured by Nail Psoriasis Severity Index (NAPSI) at week-24. The Nail Psoriasis Severity Index (NAPSI) (24) will be used for evaluating the fingernails and toenails of subjects with PRP. This is expected to be useful tool because nails in PRP have many overlapping features with psoriasis including nail plate crumbling, splinter hemorrhages, nail oil drop (yellow-brown) discoloration, and nail bed hyperkeratosis, although PRP nails are less likely to have onycholysis and red spots in the lunula (25).

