3.2.3. Secondary Endpoints Assessed by Subject

 Proportion of subjects achieving a 4-point improvement in quality of life measured by the Dermatology Life Quality Index (DLQI) at week-24, proportion of patients achieving a DLQI of 0 or 1 at week-24, and mean improvement in DLQI score at week-24. The DLQI (26) is a validated tool for inflammatory skin conditions. It is a 10-question survey, scored 0 – 30 points. For inflammatory skin conditions, a 4-point change in DLQI score is considered clinically important (27).

- Mean percentage in improvement in Psoriasis Symptoms and Signs Diary (PSSD) at week-24, and proportion of patients achieving a PSSD of zero at week-24. The PSSD is an 11-question 0 – 10-point numeric rating scale (NRS) patient-reported outcome measure assessing itch, dryness, cracking, skin tightness, scaling, shedding or flaking, bleeding, burning, stinging, and pain over the last 24 hours and 7 days respectively (28).
- Mean change from baseline individual PRP Area and Severity Index (iPRPASI) at week-24 after treatment with guselkumab, and correlation of subject-assessed iPRPASI scores with investigator-assessed PASI scores. The IPRPASI is a novel subject self-assessment score of disease involvement and severity, based on a previously published similar tool validated for psoriasis (29).
- Sustained remission at week-36, 16 weeks after the last guselkumab dose, as measured by the mean change in PASI from week-24 to week-36. Sporadic PRP is often a self-limited disease, resolving spontaneously after an average of 3-6 years. Other immunomodulatory medications have induced sustained remission of PRP (22), so there is a potential that treatment may "reset" the immune response and lead to long-term improvement in the disease, especially in subjects without genetic mutations. Subjects will be treated with guselkumab as per the FDA-approved psoriasis treatment guidelines, and therapy will be stopped after the 20-week dose. Subjects will be monitored at 24 weeks (primary study endpoint) and then at 36 weeks to assess for sustained remission versus relapse.

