4. STUDY ENROLLMENT AND WITHDRAWAL

4.1. Inclusion criteria

- Diagnosis of PRP by clinical assessment and biopsy.
- Male subject age 18-99, willing to use a reliable form of birth control if sexually active with a woman who is able to become pregnant.
- Female subject age 18-99; either of non-childbearing potential or of childbearing potential who test negative for pregnancy and agree to use a reliable method of birth control or remain abstinent during the study and for at least 12 weeks following the last dose of guselkumab.
- Involved BSA ≥ 10% at baseline.
- Are a candidate for phototherapy and/or systemic therapy.
- Willingness to travel to OHSU for all study visits, or willing/able to participate in remote videoconferencing visits with access to a computer with internet capabilities and webcam.
- Have given written informed consent approved by the OHSU Investigational Review Board.

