7.2.1. Primary Endpoint Analysis

• Mean improvement from baseline PASI at week-24 will be analyzed for statistical significance using a paired, two-tailed Student's t-test.

7.2.2. Secondary Endpoint Analyses:

- Time (weeks) to improvement by 50% in the PASI score (PASI 50) will be reported as a mean with standard deviation and also represented graphically.
- Mean improvement from baseline BSA at week-24 will be analyzed for statistical significance using a paired, two-tailed Student's t-test.
- The proportion of subjects achieving a Physician's Global Assessment of 0 or 1 at week-24 will be reported as a proportion, and compared with historical estimates of treatment success with acitretin and methotrexate (1).
- The proportion of subjects achieving a Palmoplantar Physician's Global Assessment of 0 or 1 at week-24 will be reported as a proportion.
- The mean improvement in nail involvement measured by NAPSI (see below) at week-24 will be analyzed for statistical significance using a paired, two-tailed Student's t-test.
- The proportion of subjects achieving a 4-point improvement in DLQI and the proportion of subjects achieving a DLQI score of 0 or 1 at week-24 will be reported as proportions. The mean

improvement in DLQI score from week-0 to week-24 will be analyzed using a paired, two-tailed Student's t-test.

• The mean improvement in PSSD at week-24 will be analyzed for statistical significance using a paired, two-tailed Student's t-test. The proportion of subjects achieving a PSSD of zero at week-24 will be reported as a proportion.

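### PPPGA success at week 24 carries no baseline condition, and NAPSI and PSSD are worded on different scales in section 3 and section 7.2.2

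*Combined protocol and SAP*

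**What the plan says.** **PPPGA.** Section 3.2.2 makes PPPGA 0 or 1 at week 24 a secondary endpoint and explains why palms and soles get their own measure: "Palmoplantar disease will be assessed separately from overall disease since it has high morbidity and may respond differently to therapy". The analysis in section 7.2.2 is one sentence: "The proportion of subjects achieving a Palmoplantar Physician's Global Assessment of 0 or 1 at week-24 will be reported as a proportion". No test, historical comparison, denominator or baseline condition is attached. The severity criterion for entry in section 4.1 is "Involved BSA ≥ 10% at baseline", and the synopsis agrees. Neither list has a palmoplantar or nail criterion. PPPGA and NAPSI are both recorded at week 0 (5.1.4) and week 24 (5.1.9).

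**NAPSI and PSSD.** Section 3.2.2 defines the nail endpoint as "Mean percentage improvement in nail involvement measured by Nail Psoriasis Severity Index (NAPSI) at week-24". Section 3.2.3 defines the symptom endpoint as "Mean percentage in improvement in Psoriasis Symptoms and Signs Diary (PSSD) at week-24". Section 7.2.2 then says "The mean improvement in nail involvement measured by NAPSI (see below) at week-24 will be analyzed for statistical significance" with a paired, two-tailed t-test, and treats PSSD in the same way. It mentions no percentage for either. The pointer attached to NAPSI there leads to no further text on the scale.

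**The concern.** A week-24 status measures response only in subjects who could change into that status. Overall PGA is partly protected, because everyone enters with at least 10% of body surface involved. Nothing comparable protects PPPGA. In a single-arm trial no control group separates subjects who cleared from subjects who had little palm or sole disease to begin with. That blurs the quantity section 3.2.2 wants to see, which is whether palms and soles respond differently.

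The scale question is separate. Mean percentage improvement and mean raw improvement are different summaries and can disagree. A subject-level percentage is also undefined when the baseline score is 0. Entry allows that, since it sets no nail criterion and no minimum symptom score. Section 7.2 has the PI analysing data throughout an open-label trial, so the scale should be fixed before results could steer the choice.

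**Working it through.** **The plan's own figure.** The plan computes no figure for PPPGA, NAPSI or PSSD. Its only design calculation is the PASI power table in 7.1. The exact noncentral t with 9 degrees of freedom and noncentrality (8/8)×√10 = 3.162, at two-sided 0.05, gives 0.8031, as printed. This point does not touch that figure.

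**PPPGA inputs.** N = 15 is from 7.1. The documents do not give the next three, so they are assumptions shown over a range:
- k, the number of subjects at PPPGA 0/1 at baseline
- s, the share of those still at 0/1 at week 24
- r, the week-24 response rate in subjects involved at baseline

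All-subject rate = [k·s + (15−k)·r]/15. Subtracting r gives the bias, k(s−r)/15. In percentage points:

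| k | s=1: r=0 / 40% / 80% | s=0: r=0 / 40% / 80% |
|---|---|---|
| 0 | 0 / 0 / 0 | 0 / 0 / 0 |
| 1 | +6.7 / +4.0 / +1.3 | 0 / −2.7 / −5.3 |
| 2 | +13.3 / +8.0 / +2.7 | 0 / −5.3 / −10.7 |
| 3 | +20.0 / +12.0 / +4.0 | 0 / −8.0 / −16.0 |

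The maximum per baseline-clear subject is 1/15 = 6.7 points, or 1/10 = 10.0 points at the 10-subject minimum in 7.1.

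**Worked case.** Take k = 3 and three responders among the 12 involved subjects. The involved-subject figure is 3/12 = 25.0% (exact 95% CI 5.5 to 57.2).
- If all three baseline-clear subjects stay clear, the all-subject figure is 6/15 = 40.0% (16.3 to 67.7), 15 points higher.
- If none does, it is 3/15 = 20.0% (4.3 to 48.1), 5 points lower.
- With k = 0 the two figures are the same.

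**Scale.** Take two invented subjects whose mean PSSD item scores go from 1 to 0 and from 8 to 6.
- Mean of individual percentages: (100 + 25)/2 = 62.5%.
- Mean raw change: (1 + 2)/2 = 1.5, which is 1.5/4.5 = 33.3% of the mean baseline of 4.5.

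An invented ten-subject set shows that the test can move too. Baselines are 80, 60, 40, 20, 10, 8, 4, 4, 2, 2 and week-24 scores are 40, 30, 20, 10, 5, 8, 6, 6, 3, 3. Mean raw change is 99/10 = 9.9 (paired t, p = 0.07). The mean percentage improvement is (5×50 + 0 − 4×50)/10 = 5% (one-sample t, p = 0.76). These sets were built to show that divergence is possible; they do not predict it.

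**Does NAPSI need its own involved-subject test?** Assume raw change in involved subjects has mean 1 and SD 1, and k = 3 subjects with no nail disease contribute zeros. Over all 15, the mean is 0.800, the SD 0.978, t = 3.17 and p = 0.0069. Over the 12 involved, t = √12 = 3.46 and p = 0.0053. The planned test barely changes.

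**The case against.** **The denominator.** The text says subjects, not all subjects, and achieving a grade could be meant as a change of state. A reader might infer that the plan chose an all-subject denominator. It did not; it is silent. That denominator is only the plain reading, because no subset or change rule is given. Nor do the criteria exclude palmoplantar disease; they simply do not ask for it.

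**The direction.** A reader might also infer that the PPPGA result will be inflated. The documents do not support that. Section 1.1 lists "painful thickening and cracking of the palms and soles, hair loss, crumbling nails" among the features of PRP, so k may well be 0. Where k is above 0, the bias can be zero or negative. In the worked case the shifts lie well inside the confidence intervals, and no test or decision rests on PPPGA. All of this stands, and it limits the weight of the point.

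**The scale.** A percentage summary beside a t-test on raw scores is a coherent pairing, and a percentage computed as mean change over mean baseline exists even if one subject scores 0. So the two sections need not be in flat contradiction. Still, neither section says which reading applies, and the readings can give different results.

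**Consistency.** DLQI 0/1 and PSSD of zero at week 24 are equally unconditioned on baseline. That is fair. PPPGA is singled out because the protocol itself gives a reason to isolate the palmoplantar response.

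**Late remedy.** The week-0 and week-24 data will exist, so the table could be produced at reporting without an amendment. That is true, but a denominator and a scale fixed in advance are worth more than ones chosen after the results are seen.

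**Conclusion.** The point holds as a minor one about secondary endpoints. As worded, PPPGA 0/1 at week 24 mixes response with baseline status for any subject who enters at 0/1. The size is k(s−r)/15. For k = 3 it runs from +20.0 points (s = 1, r = 0) to −16.0 points (s = 0, r = 80%), and it is nil if k = 0. The values of k, s and r are assumptions.

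NAPSI and PSSD lack a single stated scale, and a subject-level percentage has no rule for a baseline of 0.

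Two further inferences are not supported. Subjects without nail disease do not undermine the NAPSI test: under the assumptions above, p is 0.0069 against 0.0053 at k = 3, so no separate NAPSI subset analysis is called for. The primary PASI analysis and the sample size are unaffected.

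**What to change.** - **PPPGA (3.2.2 and 7.2.2).** Report 0/1 at week 24 among subjects with baseline PPPGA of 2 or more, as n/N with an exact 95% CI. Show it beside the all-subject figure and a baseline-by-week-24 table, which also reveals new involvement. The cut means only that the subject is not already a success, so it needs no further definition of the grades.
- **NAPSI and PSSD (3.2.2, 3.2.3 and 7.2.2).** Define both as raw change from baseline, matching the paired t-test. Keep any percentage descriptive and limit it to subjects with a baseline above 0.

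The cost is a short amendment, which section 10.6 routes through Janssen Scientific Affairs and then the IRB. No new data are needed: PPPGA and NAPSI are already taken at weeks 0 and 24, and PSSD at every visit from week 0. The downside is a smaller denominator and a wider interval for the PPPGA subset, with some regression to the mean because it is selected on baseline involvement. Keeping the all-subject figure alongside offsets this.

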5.1.4. Visit 1 / Week-0 (baseline)

Visit 1 will be performed at OHSU for all subjects.

- Study personnel will gather the following information from the subjects and record the results in REDCap:
 - Demographics (sex, gender, race, ethnicity)
 - Current medications
 - Drug allergies
 - Use of alcohol, tobacco, and other substances
 - PRP medical history
 - General medical history and adverse events since screening
 - Family medical history
 - Review of Systems
 - Height and weight
 - Blood pressure
 - Pulse
- Subjects will enter the following information about their disease and medical history via OHSU REDCap survey:
 - DLQI
 - PSSD
 - iPRPASI
- The subject will be clinically examined by an investigator (clinician or research nurse) who will assess the following and record the results in OHSU REDCap:
 - Full body skin exam with documentation of PASI, PGA, PPPGA, and NAPSI
 - Examination of the oral mucosa
 - Heart and lung auscultation
 - Palpation of the cervical, axillary, and inguinal lymph nodes
 - Presence of peripheral edema
- Photographs will be taken using a high-resolution digital camera of all body regions against a dark backdrop to visually record extent of disease. Subjects will assume standardized poses according to published recommendations (*31*), with the addition of focused photographs of the palms and nails.
- Subjects will undergo a punch biopsy (consisting of three adjacent 3 mm punch biopsies, a total surface area equivalent to the size of a 5 mm punch biopsy) from affected skin, performed by an

investigator. One additional 3 mm punch biopsy will be obtained from non-lesional skin as a control if non-lesional skin is available. For consistency, skin of back will be chosen for biopsy if an affected site is available. If back skin is not available, alternate sites in order of preference will include: chest, arm, leg. Location of the biopsy will be carefully documented.

- Blood will be drawn for measuring levels of inflammation
- A saliva sample will be collected for genetic analysis
- The first dose of 100 mg of subcutaneous guselkumab will be administered by trained study personnel while the study subject undergoes teaching for future self-administration.
- Subjects who plan to complete future visits by videoconferencing will receive a scale and sphygmomanometer for future vital sign assessments

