5.1.5. Visit 2 / Week-4 (28 days +/- 4 days after last visit)

Visit 2 will be performed at OHSU for all subjects.

- Study personnel will gather the following information from the subjects and record the results in REDCap:
 - Change in medications since the last visit
 - Change in drug allergies since the last visit
 - Change in personal or family medical history since the last visit, including adverse events
 - Weight
 - Blood pressure
 - Pulse
- Subjects will enter the following information about their disease and medical history via OHSU REDCap survey:
 - DLQI
 - PSSD
 - iPRPASI
- The subject will be clinically examined by an investigator (clinician or research nurse) who will assess the following:
 - Full body skin exam with documentation of PASI, PGA, and PPPGA
- Photographs will be taken against a dark backdrop with standardized poses according to published recommendations (*31*), with the addition of focused photographs of the palms and nails.
- Subjects will undergo a punch biopsy (consisting of three adjacent 3 mm punch biopsies, a total surface area equivalent to the size of a 5 mm punch biopsy) in the same body region as the first documented biopsy (back, chest, arm, or leg)
- The second dose of 100 mg of subcutaneous guselkumab will be administered by the subject with observation and teaching from study personnel.
- Blood will be drawn for monitoring the CBC, CMP, and measuring levels of inflammation

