7. STATISTICAL CONSIDERATIONS

7.1. Sample Size Computation and Power Analysis

This is a pilot study with no published baseline data; thus a power analysis was performed with the following rough assumptions. With measurement of the mean paired difference in PASI score before and after treatment of a minimum of 10 subjects, we would have 80% power at the 0.05 level to detect a mean within-subject change of 8-points when the standard deviation is 8-points. Due to the uncertainty inherent with a pilot study, the goal number of subjects with PRP who will be recruited for the study is 15.

				Mean Change	Standard
Power (1-ß)	Sample Size	а	ß	in PASI	Deviation
0.9998	10	0.05	0.0002	-8	4
0.9940	10	0.05	0.0060	-8	5
0.9621	10	0.05	0.0379	-8	6
0.8942	10	0.05	0.1058	-8	7
0.8031	10	0.05	0.1969	-8	8
0.9873	10	0.05	0.0127	-6	4
0.9203	10	0.05	0.0797	-6	5
0.8031	10	0.05	0.1969	-6	6
0.6755	10	0.05	0.3245	-6	7
0.5620	10	0.05	0.4380	-6	8

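### Palmoplantar disease is analysed only as an uncompared week-24 proportion with PPPGA 0 or 1, so the grades collected at baseline and over time are unused and improvement in the palms and soles is not estimated

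*Combined protocol and SAP*

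**What the plan says.** Section 3.2.2 gives the reason for a separate palmoplantar endpoint: "Palmoplantar disease will be assessed separately from overall disease since it has high morbidity and may respond differently to therapy". It defines the endpoint as "Proportion of subjects achieving a Palmoplantar Physician's Global Assessment (PPPGA) of 0 or 1 at week-24". Section 7.2.2 gives the whole analysis: "The proportion of subjects achieving a Palmoplantar Physician's Global Assessment of 0 or 1 at week-24 will be reported as a proportion". It specifies no test, interval, comparison with baseline or historical comparator. Overall PGA 0/1, by contrast, is to be set against historical estimates.

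The grade is collected throughout. The week-0 and week-24 examinations (5.1.4, 5.1.9) call for "Full body skin exam with documentation of PASI, PGA, PPPGA, and NAPSI". The week 4, 8, 12, 20 and 36 examinations call for "Full body skin exam with documentation of PASI, PGA, and PPPGA". That is seven assessments per subject.

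The severity criterion for entry (4.1) is "Involved BSA ≥ 10% at baseline". No minimum palmoplantar grade is required.

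In sections 7.2.1 and 7.2.2, PASI, BSA, NAPSI, DLQI and PSSD each get a paired comparison with baseline. DLQI and PSSD get both a threshold proportion and a mean change.

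**The concern.** The hypothesis in section 1.2 is about improvement. For the palms and soles, the plan describes only an end state. A subject who moves from the worst grade to grade 2 is counted with one who does not change or who worsens. A subject already at 0 or 1 before the first injection is counted as having achieved the endpoint.

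Overall PGA is also cut at 0/1, but overall skin keeps a full-scale analysis through PASI and BSA, and nails keep one through NAPSI. The palms and soles have no such second measure. No other endpoint is described as isolating them, and no analysis of the palm photographs is planned.

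At stake is the question the protocol itself raises, whether this site responds differently. With about 15 subjects, a clear-or-almost-clear percentage with no baseline beside it answers that poorly. Section 1.1 says PRP has no established severity guidelines, and the documents cite no outside requirement for this cut.

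**Working it through.** **1. The plan's own figure.** Section 7.1 states that, with 10 subjects, "we would have 80% power at the 0.05 level to detect a mean within-subject change of 8-points when the standard deviation is 8-points". For a paired two-sided t-test, df = 9 and the noncentrality is (8/8)×√10 = 3.162. Power from the noncentral t is 0.8031, as tabulated, and the other nine rows reproduce to within 0.0001. At n=15 the same inputs give 0.949. This covers PASI only; no power or precision figure is given for PPPGA.

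**2. What the planned proportion can show.** Recruitment: "the goal number of subjects with PRP who will be recruited for the study is 15". Exact (Clopper-Pearson) 95% intervals at n=15 are:
- 0/15: 0 to 22%
- 2/15: 2 to 40%
- 5/15: 12 to 62%
- 8/15: 27 to 79%

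If all 15 subjects went from grade 4 to grade 2, the report would read 0/15, the same as if none had changed. In the other direction, if 30% start at 0/1 and there is no effect, a simulation still gives about 31% at week 24.

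**3. How much information the cut discards (illustrative).** The documents give no PPPGA scale, baseline distribution or effect, so all of these are assumptions:
- scale 0-4; baseline grades 2, 3 and 4 equally likely; results clipped to 0-4
- main case: change of +1/0/-1/-2/-3 in 5/25/50/15/5% of subjects, mean 0.05 - 0.50 - 0.30 - 0.15 = -0.90
- smaller case: +1/0/-1/-2 in 10/35/40/15%
- larger case: 0/-1/-2/-3 in 10/20/40/30%, mean about -1.8

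Chance q of reaching 0/1, averaged over baseline grades 2, 3 and 4:
- main: (0.70 + 0.20 + 0.05)/3 = 0.317
- smaller: (0.55 + 0.15 + 0)/3 = 0.233
- larger: (0.90 + 0.70 + 0.30)/3 = 0.633

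Paired 0/1 comparison (exact McNemar): everyone starts at 2 or more, so k subjects crossing the cut give p = 2×0.5^k. Five give 0.0625 and six give 0.031, so at least six are needed. Power is P(X ≥ 6) with X ~ Binomial(n, q).

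Graded comparison: exact two-sided signed-rank test on grade change (zeros dropped, mid-ranks), by simulation. Repeat runs differ by one to two points.

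| Case | n | Graded change | 0/1 cut |
|---|---|---|---|
| Main | 15 | 95-96% | 33% |
| Main | 12 | 85-86% | 14-15% |
| Main | 10 | 71-73% | 6% |
| Smaller | 15 | 67% | 11% |
| Smaller | 10 | 34-36% | 1-2% |
| Larger | 15 | 100% | 98% |
| Larger | 12 | 100% | 89-90% |
| Larger | 10 | 100% | 71% |

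**4. Small evaluable numbers.** With no palmoplantar entry criterion, fewer than 10 subjects may have baseline PPPGA of 2 or more. In the main case, signed-rank power is about 48% at n=8, 31% at n=7, 12% at n=6 and zero at n=5, where the smallest attainable two-sided p is 2×0.5^5 = 0.0625.

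**The case against.** The strongest reply has four parts.

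- **No PPPGA test is planned.** The 33% and 6% belong to a comparison added here for illustration. This stands. A reader might infer that the trial contains an underpowered palmoplantar test. It does not; it contains a description that leaves out the baseline.
- **The gap depends on the assumed effect.** This also stands. A reader might infer that graded analysis always gains a third or more in power. That is true only for the modest effects. Section 1.1 points to larger ones: 84-85% clear or almost clear in psoriasis, and marked improvement in 90% of PRP cases given p40 inhibition. Neither figure is specific to palms and soles, but with a change of about two grades the n=15 gap is about 2 points.
- **Nothing is lost.** A reader might infer that the trial cannot show palmoplantar improvement at all. The grades will be in the database, and nothing bars a later shift table. But section 7.2 has the PI analysing data throughout an open-label trial, so a graded analysis chosen later would look data-driven.
- **The 0/1 cut is interpretable, and this is a secondary endpoint in a single-arm pilot.** Both are fair, and they argue for keeping 0/1. Section 3.2.3 also says sporadic PRP is often self-limited, so a significant within-subject change would not by itself attribute improvement to guselkumab.

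**Conclusion.** The concern holds as a loss of information. The one domain that the protocol sets apart as possibly responding differently is reported as an uncompared week-24 proportion, and no planned analysis uses the baseline or serial grades. The planned analysis therefore does not estimate palmoplantar improvement and treats partial response as no response.

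The size cannot be fixed from the documents. Under the assumed scale, baseline mix and mean change of about -0.9 grade, graded change is far more informative than the cut at n=10 to 15 (about 96% against 33%, and 73% against 6%). The advantage nearly disappears at n=15 with changes of about two grades, and the graded test itself is weak below about 8 evaluable subjects. The primary endpoint and its power calculation are unaffected. This is a cheap improvement to a secondary analysis, not a flaw in the trial's main conclusion.

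**What to change.** In sections 3.2.2 and 7.2.2, keep the proportion with PPPGA 0 or 1 at week 24. Add, for subjects with baseline PPPGA of 2 or more:

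- a table of baseline grade by week-24 grade
- the numbers improved, unchanged and worse
- the within-subject change in grade from week 0 to week 24, tested with an exact two-sided Wilcoxon signed-rank test and labelled a supportive secondary analysis
- the evaluable n, so that a non-significant result on few subjects is read as such

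An exact 95% interval for the 0/1 proportion would also help. Put the wording in place before week-24 data are examined.

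The cost is SAP text and one extra analysis of data already collected, with no new visit or assessment. The downside is one more secondary p-value, possibly on few subjects, in an uncontrolled pilot.
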